# 7. INTERIM ANALYSES

# 7.1.1. Interim Analysis for Futility and Efficacy

An interim analysis for both futility (non-binding) and efficacy will be conducted on ORR by BICR for Cohort A based on the first 90 participants enrolled (Interim Analysis Evaluable Set A) and treated in that cohort and for Cohort B based on the first 30 participants enrolled and treated in that cohort (Interim Analysis Evaluable Set B). Each respective interim analysis will occur no earlier than the point at which all early responders (ie, those who respond within the first 3 post-baseline assessments) among the participants to be included have had their responses confirmed.

The interim analyses in both cohorts will be based on the primary endpoint of ORR by BICR. The decision rules are described in Section 5.1.2.

The interim analyses will be performed by an independent statistician. Unblinded results from the interim analyses will not be communicated to the Sponsor's clinical team or to any party involved in the study conduct (apart from the independent statistician and E-DMC members) until the E-DMC has determined that either (i) the analysis has crossed the pre-specified boundary for efficacy or (ii) the study needs to be terminated due to any cause. Further details will be described in the E-DMC charter.

The final analyses will be performed by the Sponsor's clinical team.

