## 4. ANALYSIS SETS (POPULATIONS FOR ANALYSIS)

For purposes of analysis, the following analysis sets are defined:

Defined Analysis Set	Description
Safety Analysis Set	The safety analysis set in each cohort will include all enrolled participants in the respective cohort who received at least one dose of study intervention. This will be the primary analysis population for evaluating participant characteristics, treatment administration/compliance and safety endpoints.
Final Analysis Evaluable Set	The final analysis evaluable set in each cohort will include all enrolled participants in the respective cohort who received at least one dose of study intervention. This will be the primary analysis population for evaluating efficacy endpoints. This is the same as the safety analysis set thus only the "safety analysis set" terminology will be used.
Interim Analysis Evaluable Set A	The interim analysis evaluable analysis set A will include the first 90 enrolled participants who received at least one dose of study intervention in Cohort A. This will be the primary analysis population for evaluating efficacy endpoints at the interim analysis for Cohort A.

Interim Analysis Evaluable Set B	The interim analysis evaluable analysis set B will include the first 30 enrolled participants who received at least one dose of study intervention in Cohort B. This will be the primary analysis population for evaluating efficacy endpoints at the interim analysis for Cohort B.
PK Analysis Set	The PK analysis set is a subset of the safety analysis set and will include participants who have at least one postdose concentration measurement.
Immunogenicity Analysis Set	The immunogenicity analysis set is a subset of the safety analysis set and will include participants who have at least one sample tested for ADA.
Biomarker Analysis Set	The biomarker parameter analysis set in each cohort is a subset of the safety analysis set and will include participants who have at least one baseline biomarker assessment.
	Analysis sets will be defined separately for biomarkers based on blood, saliva, and bone marrow samples.
PRO Analysis Set	The PRO analysis set in each cohort will include all participants in the safety analysis set who completed a baseline (last PRO assessment prior to or on the first dose of study intervention) and at least one post-baseline PRO assessment.

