An interim analysis for both futility (non-binding) and efficacy will be conducted on ORR by BICR for Cohort A based on the first 90 participants enrolled and treated in that cohort, and for Cohort B based on the first 30 participants enrolled and treated in that cohort. Each respective interim analysis will occur no earlier than the point at which all early responders (ie, those who respond within the first 3 post-baseline assessments) among the participants to be included have had their responses confirmed.

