## 5.1.2. Decision Rules

An interim analysis for both futility (non-binding) and efficacy will be conducted for the primary endpoint for Cohort A and Cohort B. At the time of the interim analysis, the testing rule based on an exact binomial test will depend on the actual number of participants included in the analysis for each cohort with sufficient follow-up.

At the time of the SAP amendment, enrollment had exceeded the 120 Cohort A and 60 Cohort B participants. At the time of the final analysis, the testing rule based on an exact binomial test will depend on the exact number of participants enrolled and treated in each cohort, respectively. Operating characteristics (Type I and Type II error) were calculated using the exact binomial distribution based on the current enrollment (see below). It can be noted that the futility and efficacy stopping boundaries for both cohorts at the interim analysis are equivalent to what would be induced if using the rho family beta-spending boundary with parameter = 3 and the rho family alpha-spending boundary with an exact binomial test.

At the interim analysis for each cohort, accrual may be stopped for further evaluation due to futility; otherwise, the cohort will proceed as planned to the final analysis, and all ongoing participants will continue with scheduled visits per the schedule of activities in the protocol.

At the time of the SAP amendment, 94 Cohort A participants were initially dosed at least 4 months prior to the data cutoff and will be included in the interim analysis. The interim analysis will include a few participants with EMD at baseline who have insufficient follow-up for confirmed response. No interim analysis will be performed for Cohort B participants as not enough participants have adequate follow-up since Cohort B has a higher incidence of EMD at baseline compared to Cohort A. The boundaries at the final analysis for Cohort B do not change if no interim analysis is performed.

Cohort A: Operating Characteristics								
	Futility Criteria (responders/patients)	Efficacy Criteria (responders/patients)	Cumulative alpha spent*	Cumulative beta spent**				
Interim Analysis	≤33/94	≥41/94	0.0036	0.0078				
Final Analysis	≤47/123	≥48/123	0.0207	0.0204				

\* Cumulative alpha spent calculated assuming the null ORR of 0.30.

\*\* Cumulative beta spent calculated assuming the target ORR of 0.48.

Cohort B: Operating Characteristics							

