#### 6.6.2. Study Conduct and Participant Disposition

#### 6.6.2.1. Disposition

The percentages below will be calculated based on the number of participants in the Safety Analysis Set (unless specified otherwise) and summarized by cohort and overall.

- Number of participants enrolled and treated by country and site;
- Number and percentage of participants in each of the analysis sets defined in Section 4 based on all enrolled participants;
- Number and percentage of enrolled participants with study intervention ongoing, discontinued or not given;
- Number and percentage of enrolled participants who discontinued study intervention, overall and by the main reason for discontinuation of study intervention;
- Number and percentage of participants who discontinued follow-up, overall and by the main reason for discontinuation of follow-up. Participants without a follow-up disposition CRF who died, were lost to follow-up, or withdrew consent during treatment will have their treatment discontinuation reason displayed as their follow-up discontinuation reason.

In addition, dispositions related to COVID-19 may be presented in a separate listing if there is significant impact of COVID-19.

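### Does leftover first-90 and first-30 interim wording leave the interim analysis without a clear population or boundary?

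*SAP*

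**What the plan says.** **Older wording, still in the body text.** SAP Section 4 states that the Cohort A interim "set A will include the first 90 enrolled participants who received at least one dose of study intervention in Cohort A". Protocol Section 9.3 has the same definition, and both documents also keep an interim set of the first 30 in Cohort B. SAP Section 5.1.1 repeats the plan, including a look "for Cohort B based on the first 30 participants enrolled and treated in that cohort". SAP Section 7.1.1 places the Cohort A look on "the first 90 participants enrolled (Interim Analysis Evaluable Set A").

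**Newer wording.** SAP Section 5.1.2 reports that "94 Cohort A participants were initially dosed at least 4 months prior to the data cutoff and will be included in the interim analysis", and that "No interim analysis will be performed for Cohort B participants". Its Cohort A table has boundaries only for 94 at the interim (33 or fewer, 41 or more) and 123 at the final (48 or more). Its Cohort B table still shows an interim row with an efficacy value of 13 of 30, above the final rule of 16 of 64.

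**The link between them.** SAP Section 7.1.1 says of the rules: "The decision rules are described in Section 5.1.2".

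**The protocol.** Section 9.5.1 first gives planning thresholds: 31 or fewer and 38 or more of 90 in Cohort A, 3 or fewer and 11 or more of 30 in Cohort B. It then says that the rule depends on the number actually included, moves Cohort A to 94 with boundaries 33 and 41, and cancels the Cohort B interim.

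**The concern.** Read alone, SAP Section 7.1.1 names a population of 90 and points to a section with no rule for 90. The only efficacy threshold out of 90 is the protocol's 38. For Cohort B, some sections promise a look and another cancels it, and the two documents print different efficacy values for that look (11 and 13 of 30).

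Three things could be at stake.

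- **Type I error**, if a planning threshold were applied in place of the one in force.
- **Release of interim results.** SAP Section 7.1.1 withholds unblinded results "until the E-DMC has determined that either (i) the analysis has crossed the pre-specified boundary for efficacy" (or that the study must be terminated), so it matters which boundary that is.
- **A required table.** SAP Section 6.6.2.1 asks for "Number and percentage of participants in each of the analysis sets defined in Section 4 based on all enrolled participants". Programmed literally, it would report interim sets of 90 and 30, neither of which is the population analysed.

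**Working it through.** **Inputs.** One-sided alpha is 0.025 per cohort, by exact binomial test (SAP Section 6.1.1). Null ORRs are 0.30 (A) and 0.15 (B), and target ORRs are 0.48 and 0.34 (SAP Section 5.1.2). Efficacy spending is rho-family with parameter 5 (protocol Section 9.5.1). Final numbers are 123 and 64.

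**Step 1: reproduce the SAP's Cohort A figures.** Interim alpha is P(X ≥ 41 | 94, 0.30) = 0.0036. Total alpha, with futility non-binding, adds the sum over x ≤ 40 of P(X94 = x) × P(Y29 ≥ 48 − x), where Y29 is the number of responders among the remaining 123 − 94 = 29. The result is 0.0207. With futility applied, beta at ORR 0.48 is 0.0078 at the interim and 0.0204 in total. All four match the SAP.

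**Step 2: is 41 of 94 the declared boundary?** The allowance is 0.025 × (94/123)^5 = 0.0065. A threshold of 41 spends 0.0036 and fits. A threshold of 40 spends 0.0066 and does not. So 41 is the correct exact boundary.

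**Step 3: Cohort B.** With no interim, P(X ≥ 16 | 64, 0.15) = 0.0248. With the tabulated 13 of 30 the total is also 0.0248, because that look spends only 0.0002. This supports the SAP's statement that the final boundary does not depend on whether the look is held.

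**Step 4: where the protocol's planning values come from.** A normal-approximation boundary is n·p0 + z·√(n·p0·(1 − p0)), with z set by the spending allowance.

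- Cohort A, 90 of 120: the allowance is 0.025 × 0.75^5 = 0.0059. The mean is 27 and the SD is √18.9 = 4.35. The boundary is 37.94, rounded up to 38.
- Cohort B, 30 of 60: the allowance is 0.025 × 0.5^5 = 0.00078. The mean is 4.5 and the SD is √3.825 = 1.96. The boundary is 10.69, rounded up to 11.

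On the exact scale these thresholds spend 0.0092 and 0.0029, more than the allowances. The exact boundaries would be 39 of 90 (0.0050) and 13 of 30 (0.0002). The planning values therefore fit an earlier normal-approximation calculation. That agrees with the change histories, in which protocol Amendment 7 moved to a normal distribution and SAP version 5 went back to the exact method.

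**Step 5: what if a planning value were used with the final rule in force?**

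| Cohort | Interim rule | Final rule | Total one-sided alpha |
|---|---|---|---|
| A | 41 of 94 (in force) | 48 of 123 | 0.0207 |
| A | 38 of 90 (planning) | 48 of 123 | 0.0232 |
| B | none (in force) | 16 of 64 | 0.0248 |
| B | 11 of 30 (planning) | 16 of 64 | 0.0258 |

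Only the last row exceeds 0.025, and it belongs to a look that both documents cancel.

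**Step 6: the disposition table.** Cohort A interim set: 90/123 = 73.2% as defined, 94/123 = 76.4% as analysed. Cohort B interim set: 30/64 = 46.9% as defined, not used in practice.

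**The case for a change.** The best case for an edit has three parts.

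**The definitions really do differ.** The interim set in SAP Section 4 goes by order of enrolment, while the 94 are chosen by time since first dose. Making the rule depend on the number included does not turn one set into the other. The analysis-set table was also revised later, to add the final analysis evaluable set, and the interim rows were left alone. This stands as a criticism of the drafting.

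**The two Cohort A rules can disagree.** Suppose the first 90 are among the 94 and responses are independent. The verdicts differ if X90 ≥ 38 with X94 ≤ 40, or if X90 = 37 with X94 ≥ 41. That happens in 0.6% of trials at a true ORR of 0.30, 10.6% at 0.40, 11.5% at 0.42 and 6.0% at 0.48. The figures are right, but they compare the rule in force with one that nobody is told to use. The SAP contains no threshold of 38, and protocol Section 9.5.1 replaces it with 41 of 94 within the same section. The disagreement is hypothetical.

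**The printed 11 of 30 is not harmless if taken literally**, since it would bring Cohort B to 0.0258, and it is never reconciled with 13 of 30. That too is correct. Both values lapsed when the look was cancelled, and neither enters an analysis.

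What survives is untidy text and the disposition count. SAP Section 2 already requires departures from the plan to be described in the study report. Correcting the protocol wording would mean an amendment with ethics approval (protocol Section 10.1.1) in a study that closed enrolment in January 2022, with no analytical gain.

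**Conclusion.** No change follows. This is a clerical slip: the update to 94 participants and the cancelled Cohort B look were written into the decision rules but not carried back to the set definitions. A statistician following SAP Section 7.1.1 is sent to Section 5.1.2 and finds one population and one pair of boundaries, which protocol Section 9.5.1 confirms. Those boundaries are correct under the declared spending function, and the one-sided error stays at 0.0207 in Cohort A and 0.0248 in Cohort B. The final rules, 48 of 123 and 16 of 64, agree in both documents.

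The effect is confined to one count that differs by four participants (90 or 94 of 123) and one row for a set never used. An analyst would report the 94 actually analysed, show the Cohort B interim set as not applicable, and say so in the study report.

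This rests on the interim being run as SAP Section 5.1.2 describes and on the percentages using 123 and 64 as the enrolled totals, that is, with no participant enrolled but untreated. The E-DMC charter, which holds further detail on releasing interim results, is not among the documents.

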# 7.1.2. Interim Safety Assessments

An E-DMC will review cumulative safety data during the study conduct and may make recommendations to alter the conduct of the study. In addition, the incidence of Grade 3-4 CRS, Grade 3-4 ICANS, Grade 4 treatment-related non-hematologic events (excluding CRS and ICANS), Grade 3-4 treatment-related GBS/GB-like AEs, Grade 4 treatment-related peripheral neuropathy/immune-related (IR) neurologic events (excluding ICANS), Grade 3-4 treatment-related motor neuropathy, and Grade 5 events will each be monitored throughout the study. If the number of participants observed to have such identified events exceeds a pre-specified threshold, the study will be placed on a temporary enrollment hold by the sponsor until discussions can be held with the E-DMC. During any temporary enrollment hold, no new participants can be enrolled, nor can any newly enrolled participants start study intervention. Pending E-DMC assessment, participants who have already started study intervention may continue treatment only if the benefit/risk assessment for the participant is judged to be positive by the investigator in consultation with the sponsor.

In the event that any criteria for temporary enrollment hold are met, written notification documenting the reason for temporary enrollment hold (or study termination) will be provided by the sponsor to the investigators, the ECs/IRBs, the regulatory authorities, and any CRO(s) used in the study.

The criteria for placing the study on temporary hold for safety reasons are based on Bayesian posterior probabilities. Using a non-informative Beta (0.5, 0.5) prior distribution, if the number of participants observed to have Grade 3-4 CRS results in a posterior probability that the true Grade 3-4 CRS rate exceeding 20% is  $\geq$ 0.80, the study will be put on a temporary

hold. Separate but similar criteria will be used for participants with Grade 3-4 ICANS and treatment-related Grade 4 non-hematologic events (excluding CRS and ICANS). Table 6 summarizes the minimum number of participants with such identified events that would meet the above criteria.

Table 6.	Minimum Number of Participants With Identified Events That Would
	Prompt Temporary Enrollment Hold

Number of Evaluable Participants (Cohort A + B)	10-13	14-18	19-22	23-26	27-30	31-35	36-39
Minimum number of participants with Grade 3-4 CRS events that would lead to a temporary enrollment hold*	4	5	6	7	8	9	10
Minimum number of participants with Grade 3-4 ICANS events that would lead to a temporary enrollment hold*	4	5	6	7	8	9	10
Minimum number of participants with Grade 4 treatment-related non hematologic events (excluding CRS and ICANS) that would lead to a temporary enrollment hold*	4	5	6	7	8	9	10

Prior distribution: Beta (0.5,0.5)

Criteria for 40 or more evaluable participants will be calculated such that the study will be put on temporary hold if the posterior probability that the true event rate exceeds 20% is  $\geq 0.80$ .

Evaluable participants are defined as those who have received at least 1 dose of study treatment having an identified event or those without such an event who have been followed for at least 28 days from first dose.

\* The study will be put on temporary hold as soon as the minimum number of evaluable participants with the identified AEs has reached the threshold (eg, if there are 4 participants experiencing the identified AE out of the first 6 evaluable participants, the study will be put on hold). A minimum of 4 events are required to trigger a temporary hold.

The criteria for placing the study on temporary hold for the following safety reasons are based on Bayesian posterior probabilities using a non-informative Beta (0.5, 0.5) prior distribution.

- If the number of evaluable participants observed to have treatment-related Grade 3-4 GBS/GB-like AEs results in a posterior probability that the true rate of such events exceeding 3% is ≥0.80, the study will be put on a temporary hold.
- If the number of evaluable participants observed to have treatment-related Grade 4 sensory neuropathy/other IR neurologic AEs (excluding ICANS) or treatment-related Grade 3-4 motor neuropathy results in a posterior probability that the true rate of such events exceeding 10% is ≥0.80, the study will be put on a temporary hold.

Table 7 summarizes the minimum number of evaluable participants with such identified events that would meet the above criteria.

# Table 7.Minimum Number of Participants with Identified Treatment-Related
Events That Would Prompt Temporary Enrollment Hold (GBS/GB-like
AEs, Peripheral Neuropathy/IR Neurologic AEs)

Number of Evaluable Participants	20-39	40 -64	65-90	91-	117-	145-	
(Cohort A + B)				116	144	150 a	
Minimum number of participants with	2	3	4	5	6	7	
Grade 3-4 treatment-related GBS/GB-like							
events that would lead to a temporary							
enrollment hold*							
Number of Evaluable Participants	20-27	28-35	36-43	44-52	53-60	61-69	70-78 b
(Cohort A + B)							
Minimum number of participants with	4	5	6	7	8	9	10
Grade 4 treatment-related sensory							
neuropathy/IR neurologic AE (excluding							
ICANS) or Grade 3-4 treatment-related							
motor neuropathy events that would lead							
to a temporary enrollment hold**							

Prior distribution: Beta (0.5,0.5)

a. Criteria for 151 or more evaluable participants will be calculated such that the study will be put on temporary hold if the posterior probability that the true event rate exceeds 3% is ≥0.80.

b. Criteria for 79 or more evaluable participants will be calculated such that the study will be put on temporary hold if the posterior probability that the true event rate exceeds 10% is ≥0.80.

Evaluable participants are defined as those who have received at least 1 dose of study treatment having an identified event or those without such an event who have been followed for at least 28 days from first dose.

- \* The study will be put on temporary hold as soon as the minimum number of evaluable participants with the identified AEs has reached the threshold (eg, for GBS/GB-like AEs, if there are 2 participants experiencing the identified AE out of the first 10 evaluable participants, the study will be put on hold). A minimum of 2 events are required to trigger a temporary hold.
- \*\* The study will be put on temporary hold as soon as the minimum number of evaluable participants with the identified AEs has reached the threshold (eg, if there are 4 participants experiencing the identified AE out of the first 15 evaluable participants, the study will be put on hold). A minimum of 4 events are required to trigger a temporary hold.

The list of search criteria for IR neurologic AE PT is defined in Appendix 3. Further clinical review is required to determine if a specific event meets the criteria.

In addition, the study will be put on temporary hold if any of the following criteria are met in the safety analysis set of the two cohorts combined:

- 1 Grade 5 event of CRS;
- 1 Grade 5 event of ICANS;
- 1 Grade 5 treatment-related peripheral neuropathy or IR neurologic event;
- Any 2 treatment-related Grade 5 events (excluding CRS, ICANS, and peripheral neuropathy/IR neurologic event).

# 9. APPENDICES

Abbreviation	Term
ADA	anti-drug antibody
ADC	antibody-drug conjugate
AE	adverse event
AESI	adverse events of special interest
ALP	alkaline phosphatase
ALT	alanine aminotransferase
aPTT	activated partial thromboplastin time prolonged
AST	aspartate aminotransferase
ASTCT	American Society for Transplantation and Cellular Therapy
ATC	anatomic Therapeutic Chemical
AUC	area under the curve
AUC last	area under the plasma concentration-time profile from time zero to the time of the last quantifiable concentration ( $C_{last}$ )
BCMA	B-cell maturation antigen
BICR	blinded independent central review
BLQ	below the limit of quantitation
BMA	bone marrow aspirate
BMI	body mass index
BOR	best overall response
C#D#	cycle # day # (eg, C1D1 = cycle 1 day 1)
CD#	cluster of differentiation # (eg, CD38)
CI	confidence interval
C max	maximum observed concentration
CR	complete response
CRR	complete response rate
CRF	case report form
CRS	cytokine release syndrome
CSE	clinical summary of efficacy
CSR	clinical study report
CTC	Common Toxicity Criteria
CTCAE	Common Terminology Criteria for Adverse Events
CV	Coefficient of variation
DI	dose intensity
DLT	dose limiting toxicity
DMC	data monitoring committee
DOCR	duration of complete response
DOMRD	duration of minimal residual disease
DOR	duration of response
ECG	electrocardiogram

